4.2.2 Labeling of plasma samples

The labels will include the following information:

Study Number: D5130C05266

Randomization/Subject Number

Visit Number: (Visit 2, 3 or 4)

Tube and Set Number (A or B)

Scheduled/Protocol Time

The label must only be used for the intended sample and the pre-printed information must not be changed.

4.2.3 Shipping of plasma samples

All PK plasma samples will be shipped via World Courier. Plasma samples will be shipped to the address below. **The 2 sets (set A and B) of plasma samples will not be shipped together in the same shipment.** Samples must be packed and shipped in accordance with the Department of Transportation (DOT) Regulation UN3373 for diagnostic specimens in compliance with International Air Transport Association (IATA) Packing Instruction 650. All applicable shipping regulations must be followed.

Samples must be placed in protective bubble wrap and then enclosed in a sealed watertight plastic bag. The sealed bag must include absorbent material to contain any leaks. The sealed bag must then be placed into a watertight TYVEC container.

The samples must be packed securely to avoid breakage during transit and packed with a sufficient quantity of dry ice to ensure they remain frozen for at least 72 hours. All applicable shipping regulations must be followed.

Documentation sufficient to identify each sample must be included in the shipment. The primary contact at AstraZeneca and the designated laboratory identified below must be notified **before samples are shipped**.

Ship samples on Saturday, Monday and Tuesday only. Do not ship on or the day before a legal holiday.

All batches of plasma samples, accompanied by the corresponding documentation, shall be addressed to:

the samples are shipped. and the recipient must be notified by phone or fax at the time

Table 2 **Schedule of PK blood sampling**

Scheduled Time Relative to Dose at Visits 2, 3 and 4	Tube and Set Number
Pre-dose (within 30 minutes of dosing)	1 A/B
0.5 hour post dose	2 A/B
1 hour post dose	3 A/B
2 hours post dose	4 A/B
3 hours post dose	5 A/B
4 hours post dose	6 A/B
6 hours post dose	7 A/B
8 hours post dose	8 A/B
12 hours post dose	9 A/B
18 hours post dose	10 A/B
24 hours post dose	11 A/B
36 hours post dose	12 A/B
48 hours post dose	13 A/B
72 hours post dose	14 A/B

4.3 Pharmacodynamic measurements

4.3.1 ADP induced platelet aggregation

Two 4.5 mL blood samples will be collected into a blue-top Vacutainer® tube which contains 3.2% 0.105M buffered citrate. These samples will be used to measure inhibition of platelet

aggregation by optical aggregometry, using 20µmol ADP as the agonist and run in duplicate, at the defined time points (see Table 3) at Visits 2, 3 and 4.

Final and maximum extent of aggregation will be recorded. Final extent of aggregation will be measured after 6 minutes or at a point where the curve has been constant for at least 1 minute. The date and time of collection will be recorded on the appropriate CRF. Details of the methods used will be agreed upon in writing by the sponsor and investigator prior to the start of the study.

Table 3 **Schedule of ADP induced platelet aggregation sampling**

Scheduled Time Relative to Dose at Visits 2, 3 and 4
Pre-Dose (within 30 minutes of dosing)
2 hours post dose
4 hours post dose
12 hours post dose
24 hours post dose

4.3.2 Bleeding time assessment

Bleeding time measurements using Simplate II[®] method will be determined at the times indicated in Table 4. Times will be recorded for each of the 2 incisions made by the device. If the pre-dose bleeding time is >9 minutes the subject should not be dosed and will be discontinued from the study.

If at the 24-hours post dose measurement the bleeding time is >60 minutes, a repeat assessment will be performed 48 hours post-dose. Additional repeat bleeding time assessments may be performed at the discretion of the investigator.

The methodology is detailed in Appendix C.

Table 4 **Schedule of bleeding time sampling**

Visit	Scheduled Time
1 (Screening)	Within 21 days prior to randomization
2	Pre-dose (within 60 minutes of dosing)
	4.5 hours post dose
	24 hours post dose
3	Pre-dose (within 60 minutes of dosing)
	4.5 hours post dose
	24 hours post dose
4	Pre-dose (within 60 minutes of dosing)
	4.5 hours post dose
	24 hours post dose

4.4 Screening and safety assessments and procedures

For timing of individual assessments and procedures refer to study plan (Table 1).

4.4.1 Informed consent

The subject's signed and dated written informed consent must be obtained before conducting any study-specific procedure.

4.4.2 Inclusion/exclusion criteria

The inclusion and exclusion criteria must be assessed and reviewed with each subject at screening and on Day -2 of Visit 2 and Day -1 of Visits 3 and 4 in order to establish and confirm his/her eligibility to participate or continue in the study.

4.4.3 Clinical laboratory measurements

Blood and urine samples will be taken for determination of clinical chemistry, hematology and urinalysis parameters. Please refer to study plan (Table 1) for the timing of individual assessments. The date and time of collection will be recorded on the appropriate CRF. The following tests will be performed:

4.4.3.1 Chemistry

Clinical chemistry assessments will include the following:

Sodium, potassium, calcium, chloride, glucose, albumin, alanine aminotransferase (ALT), aspartate aminotransferase (AST), alkaline phosphatase, blood urea nitrogen (BUN) total bilirubin, creatinine, gamma glutamyltransferase (GGT) and creatinine kinase.

4.4.3.2 Limited chemistry panel

The limited chemistry panel will consist of the following:

ALT, AST, GGT, alkaline phosphatase and total bilirubin.

4.4.3.3 Hematology

Hematology assessments will include the following:

RBC, platelets, hemoglobin, hematocrit, WBC and differential count (neutrophils, lymphocytes, monocytes, eosinophils and basophils), prothrombin time and activated partial thromboplastin time.

4.4.3.4 Urinalysis

A urine sample will be obtained for the presence of protein, glucose and blood. If positive values are reported for protein or blood, and are considered to be of clinical significance, a microscopic examination of the urine will be performed.

4.4.4 Pregnancy test-Serum and urine

Serum and urine pregnancy tests will be performed on all female subjects. The serum pregnancy test can be collected with the same sample as the blood chemistry. If the result of any pregnancy test is positive, the subject will not be allowed to proceed in the study.

Note: Although the results of the serum and urine pregnancy tests have to be documented in the subject's files, they will not be collected on the CRF's and will therefore not be recorded in the study database.

4.4.5 HIV, HBsAg and hepatitis C

A blood sample for HIV, HbsAg and hepatitis C antibody will be obtained at screening. If a test result is positive the subject will not be permitted to continue his/her participation in the study.

Note: Although the results of the HIV, HbsAg and hepatitis C tests have to be documented in the subject's files, they will not be collected on the CRF's and will therefore not be recorded in the study database.

4.4.6 Drugs of abuse screen

A urine screen for drugs of abuse will be performed on urine samples obtained from each subject. If a test result is positive for any of the substances of abuse, the subject will not be permitted to continue his/her participation in the study. The following drugs will be screened:

Amphetamines, barbiturates, benzodiazepines, cannabinoids, cocaine, methadone, opiates, phencyclidine and propoxyphene.

Note: Although the results of the urine drug screen have to be documented in the subject's files, they will not be collected on the CRF's and will therefore not be recorded in the study database.

4.4.7 Medical/surgical history

A detailed medical and surgical history including medication history will be recorded for each subject at screening. Significant medical conditions and surgical events are to be recorded on the appropriate CRF.

The medication history must identify any known drug allergies, presence or history of drug or alcohol abuse. All medications and OTC products (including vitamins and herbal remedies) taken within 2 weeks prior to dosing are to be recorded on the appropriate page of the CRF.

4.4.8 Complete physical examination

The complete physical examination will include an assessment of the following: general appearance, skin, head and neck (including eyes, ears, nose and throat), lymph nodes, thyroid, musculoskeletal/extremities (including spine), cardiovascular, lungs, abdomen and neurological (reflexes). Height (cm) and weight (kg) will be measured and BMI will be calculated. Height will be measured and BMI will be calculated at screening only.

4.4.9 Brief physical examination

The brief physical examination will include an assessment of the following: general appearance, abdomen, cardiovascular and lungs. If the subject states changes have occurred related to systems not assessed, then these systems should also be examined.

4.4.10 Resting 12-lead ECG

For timing of individual assessments refer to study plan (Table 1).

4.4.10.1 Methods of assessment

All ECGs will be evaluated by the investigator for safety as normal or abnormal. For timing of individual ECGs please refer to the study plan (Table 1). If indicated, as necessary for the safety of the subject, additional ECG assessments can be made at the discretion of the investigator.

Baseline serial ECGs will be recorded on Day -1 of Visit 2 (refer to Table 1). Serial ECGs will be recorded beginning on Day 1 of Visits 2, 3 and 4. The serial ECGs collected will be evaluated by the investigator for safety as normal or abnormal and sent to a cardiologist for centralized review by manual over-read for evaluation for QT interval measurement. Serial ECGs taken on Day -1 of Visit 2 will serve as a baseline for comparison to subsequent serial ECGs at each timepoint. The types of comparisons to be made will be discussed in the statistical analysis plan.

4.4.10.2 ECG machine

All ECGs are to be obtained using an ECG machine approved by the sponsor (25mm/sec paper speed and a voltage of 10mm/mV) that will record 12 leads simultaneously.

4.4.10.3 Electrode placement

Prior to the first ECG recording of Day -1, the location of the leads on the chest of the subject is to be marked with a water indelible pen. The investigative staff will make a reasonable effort to ensure that the leads are placed in the same location for all subsequent ECGs. Additional marks can be made with an indelible pen if needed to help ensure that the leads are placed in the same location.

4.4.10.4 Body positioning during ECG monitoring

Before starting a recording, the subject is to be in a supine position FOR AT LEAST 10 MINUTES.

4.4.10.5 Recording of ECGs

Serial ECGs are to be recorded electronically. A minimum of 5 to 7 heartbeat complexes should be recorded. Two ECGs approximately 1 minute apart will be collected at each time point for all serial ECGs.

For all ECGs, an original paper printout of the tracing must be obtained. The original tracing will be retained in the subject's file for source data verification. Additionally, 2 photocopies of each tracing will be made. One photocopy will be retained at the site in a separate file and the other copy will be available for the sponsor. Each ECG will be labeled with the study code, subject initials, enrollment/randomization number, scheduled day, scheduled time, and actual time recorded.

All ECGs will be reviewed for safety purposes by the investigator at the CRC. The time of recording of the ECG and the safety evaluation (normal/abnormal) will be recorded on the CRF. If the ECG is abnormal, a comment will be entered onto the CRF.

4.4.10.6 Determination of RR and QT intervals

A central cardiologist blinded to the study will provide an interpretation of the ECG. This will include the RR, PR, QT, and QRS intervals from serial ECGs collected on Visits 2, 3 and 4. Manual over-read of ECGs will be performed on digitized ECGs with electronic annotations.

The preferred lead to be used is Lead II, however, alternative leads (as determined by the central cardiologist) may be used if Lead II is not considered satisfactory.

Three to five complexes will be used for QT interval measurements and the mean value will be used for the estimate of QT interval. The RR interval preceding the QT interval will be measured for up to three to five complexes. The mean RR interval will also be determined.

4.4.10.7 Determination of T & U waves

The central cardiologist will assess the T wave morphology and the presence or absence of U waves will be noted.

4.4.10.8 Calculation of derivation of endpoint

ECG assessment is being conducted for safety purposes in this trial; therefore QT interval analysis is not a primary endpoint. Statistical methods applied to this analysis will be descriptive and are not intended to satisfy a hypothesis.

4.4.10.9 QT interval correction factors

The primary QTc correction will be through Bazett's formula. The Fridericia correction for QT may be applied as a secondary correction factor. Bazett and Fridericia correction for all ECGs analyzed by manual over-read will be reported in the database. The formula is shown below:

$$QTc = QT(\text{ms})/[RR(\text{sec})]^{1/2} \quad (\text{Bazett})$$

$$QTc = QT(\text{ms})/[RR(\text{sec})]^{1/3} \quad (\text{Fridericia})$$

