No serious adverse events (SAE) were observed in the 5 trials completed to date, which exposed healthy subjects to daily doses from 0.1 mg to 600 mg for periods of up to 20 days. Approximately 120 healthy subjects were entered into these trials, and 89 healthy subjects received at least 1 dose of AZD6140. Petechiae, tachycardia, and postural hypotension were the most common adverse events reported in some of these trials. However, the causal relationship of these adverse events to AZD6140 is uncertain. Four subjects in Study SC-532-5256 (single 200 mg dose study in healthy subjects) reported rashes that were considered by the investigator to have a reasonable possibility of a causal relationship to study treatment. Two of these subjects were withdrawn because of this adverse event.

In the multiple ascending dose study SC-532-5239, 1 subject had an increase in liver transaminases of more than 3 times the upper limit of normal after 4 daily doses of 300 mg AZD6140, and was discontinued from the study. The transaminases returned to normal over 24 days. Another subject had a milder increase in transaminase after 4 twice-daily doses of 200 mg that improved despite continuation and increase in dose of AZD6140. There were no other laboratory findings, and no ECG, Holter monitor or vital signs findings of concern during any of the studies.

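### Bazett is fixed as the primary QTc correction and Fridericia is optional, so a heart-rate change after dosing could distort the descriptive QTc change-from-baseline summary

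*Protocol*

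**What the plan says.** Protocol section 4.4.10.9 fixes the order of the two corrections: "The primary QTc correction will be through Bazett's formula", and then "The Fridericia correction for QT may be applied as a secondary correction factor". It gives no reason for preferring Bazett and no rule linking the choice to the heart rates observed. Both values are nevertheless to be stored: "Bazett and Fridericia correction for all ECGs analyzed by manual over-read will be reported in the database".

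Section 4.4.10.6 has a central cardiologist measure RR as well as QT. Section 6.4.3.4 then plans a descriptive summary of change from baseline in QTc for each dose and time point, without naming the correction. Section 4.4.10.8 sets the status of the analysis: "ECG assessment is being conducted for safety purposes in this trial; therefore QT interval analysis is not a primary endpoint", and "Statistical methods applied to this analysis will be descriptive and are not intended to satisfy a hypothesis".

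On heart rate, section 1.1 reports of the earlier trials: "Petechiae, tachycardia, and postural hypotension were the most common adverse events reported in some of these trials". It adds: "However, the causal relationship of these adverse events to AZD6140 is uncertain", and it reports "no ECG, Holter monitor or vital signs findings of concern during any of the studies".

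**The concern.** Because section 6.4.3.4 names no correction, its QTc summary defaults to the primary one, Bazett. Bazett divides QT by the square root of RR. If QT in these subjects varies with RR less steeply than that, Bazett over-corrects as the rate rises: QTc goes up although repolarisation has not changed. When the rate falls, QTc goes down and could hide a true prolongation.

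Tachycardia in some earlier trials makes a change in heart rate after dosing plausible, though not established. A comparison with placebo would not remove the artefact if the drug itself changed the rate.

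What is at stake is how a safety table reads. The primary objective is safety and tolerability, with 12-lead ECG among its measures. With no test or margin attached to QTc, the tabulated means are what a reader will rely on. As the text stands, a report could present Bazett summaries alone.

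**Working it through.** The protocol states no expected heart-rate change, QTc margin or QT precision, so it has no figure of its own to reproduce here. The check applies the protocol's two formulas to a drug with no effect on repolarisation.

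**Inputs from the protocol (section 4.4.10.9)**
- Bazett: QTcB = QT / RR^(1/2)
- Fridericia: QTcF = QT / RR^(1/3), with RR in seconds

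**Assumptions, not in the protocol**
- QT = 400 ms × RR^k, with k from 0.25 to 0.50
- Resting rate 60 bpm (RR = 1 s), so both corrected values start at 400 ms
- Rises of 5 to 30 bpm

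**Formulas.** With no true effect, QTcB = 400 × RR^(k − 1/2) and QTcF = 400 × RR^(k − 1/3). The apparent change is the value at the raised rate minus 400.

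**Worked case, 60 to 70 bpm, k = 1/3.** RR = 60/70 = 0.857 s. QTcB = 400 × 0.857^(−1/6) = 410.4 ms, an apparent change of +10.4 ms. QTcF = 400 × 0.857^0 = 400 ms, a change of 0.

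**Same rise, other exponents**

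| k | Bazett change (ms) | Fridericia change (ms) |
|---|---|---|
| 0.25 | +15.7 | +5.2 |
| 1/3 | +10.4 | 0.0 |
| 0.40 | +6.2 | −4.1 |
| 0.50 | 0.0 | −10.1 |

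**Other rises from 60 bpm, k = 1/3**

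| Rise (bpm) | Bazett change (ms) | Fridericia change (ms) |
|---|---|---|
| 5 | +5.4 | 0.0 |
| 10 | +10.4 | 0.0 |
| 15 | +15.2 | 0.0 |
| 20 | +19.6 | 0.0 |
| 30 | +28.0 | 0.0 |

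The starting rate matters little: a 10 bpm rise from 50, 65 or 70 bpm gives +12.0, +9.8 or +9.2 ms with Bazett at k = 1/3.

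**Falling rate.** The sign reverses. From 70 to 60 bpm at k = 1/3, QTcB goes from 410.4 to 400 ms, a change of −10.4 ms.

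**Where the two corrections are equally wrong.** On the log scale, for any given change in rate, the error is proportional to (1/2 − k) for Bazett and (1/3 − k) for Fridericia. They are equal in size when 1/2 − k = k − 1/3, so k = 5/12, about 0.42. Below that Fridericia has the smaller error; above it Bazett does.

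**The case against.** The strongest case for leaving the text alone has four parts.

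- **The exponent is unknown.** A reader might infer that any rise in heart rate must appear as QTc prolongation. The documents do not support that: they give no QT–RR exponent, and the Bazett artefact is zero at 0.50. Choosing k = 1/3 favours Fridericia by construction, since that is the one value at which it is unbiased. Above 1/3 Fridericia falls as the rate rises and could mask prolongation. This stands. The defence that Bazett merely errs towards false alarm holds only for rising rates; for falling rates it errs towards reassurance.
- **The heart-rate premise is soft.** The tachycardia was seen in some trials only, with uncertain causality and no ECG, Holter or vital-sign findings of concern. No size of change is given, so the scenarios above are illustrations. This stands too.
- **The wider harms do not follow.** A reader might infer a false ethnic difference in QTc. Section 6.4.3.4 plans no ethnic comparison of QTc, and a stable rate difference between groups would largely cancel in change from baseline. A reader might also infer that the correction could misdirect dose escalation. Section 3.1.7 has important ECG changes reviewed as a matter of judgement and states no QTc threshold, and nothing ties the over-read QTc values to that decision.
- **Much of the remedy is in place.** Both corrections are stored, RR is measured, and section 6.4.3.4 summarises all ECG intervals, so an artefact could be traced. Section 4.4.10.1 leaves the types of ECG comparison to the SAP. But section 4.4.10.9 has already settled which correction is primary, storing a value does not commit anyone to reporting it, and change from baseline is named for QTc only.

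**Conclusion.** The point holds as a limited one. The protocol fixes, without a reason, a primary correction that moves with heart rate whenever the QT–RR exponent is below 0.5, and it leaves the alternative optional. For a rise from 60 to 70 bpm with no true QT effect, the spurious change is about +10 ms at an assumed exponent of 1/3, with a range of 0 to +15.7 ms for exponents from 0.50 to 0.25. A fall in rate produces the opposite error.

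The size rests on the assumed QT–RR relation, the 400 ms reference value and a heart-rate change that the protocol does not predict. The analysis is descriptive, so no test, error rate or sample size is affected. The consequence is a safety summary that could mislead, in a study whose primary objective is safety.

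**What to change.** In section 4.4.10.9, make Fridericia the primary correction for QTc summaries and for change from baseline. State that Bazett will also be summarised as the secondary correction, so that reporting the second correction is a commitment and no longer an option. In section 6.4.3.4, name the correction used and add change from baseline in RR or heart rate beside both QTc summaries.

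No new data are needed: both corrected values are already to be stored for every over-read ECG, and RR is already measured. The cost is a small text change and a few more tables. The downside is that Fridericia is biased when the exponent is not 1/3: −10.1 to +5.2 ms for 60 to 70 bpm over exponents from 0.50 to 0.25. Showing both corrections with the heart-rate change lets a reader see when either is being driven by rate. Keeping Bazett also preserves comparison with any earlier summaries that used it; the protocol does not say which correction those used.

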4.4.11 Vital signs

The subject's sitting and orthostatic blood pressure and pulse will be recorded at the times indicated in Table 1. For each subject, throughout the study, blood pressure and pulse will be measured as follows:

Sitting

Sitting blood pressure and pulse will be measured after the subject has been sitting for 5 minutes.

Orthostatic

Orthostatic blood pressure and pulse will be measured using a blood pressure measuring device with an appropriate cuff size.

- The subject will rest in bed for 10 minutes
- Supine blood pressure and pulse is measured
- Blood pressure and pulse is then recorded again after the subject has been standing up for 2 minutes with arms hanging relaxed down on both sides.
- Any symptoms from the subject should be registered as a comment and if applicable recorded as an adverse event.

4.5 Genetic sampling and storage

A single 9 mL venous blood sample will be collected into a polypropylene EDTA tube at Visit 2 for use in genetic testing. This will be optional and the subject may choose to participate in the study but not to provide a blood sample for genetic analysis. Separate consent will be taken for genetic sampling.

The sample will be frozen as whole blood at -20°C or below in a non frost-free freezer and transported to the assaying laboratory within one month of collection. Processing, labeling and shipping instructions are provided in Appendix D.

